10.1.4 Exposure during the maintenance period for BKZ Set

Definitions for study medication duration (days) and time at risk (days) during the Maintenance Period (Week 16 to Week 56) are provided as follows:

For subjects randomized to BKZ Q4W/Q4W or BKZ Q4W/Q8W:

Study medication duration (days)

- Date of last dose of bimekizumab in the Maintenance Period – date of first dose in the Maintenance Period + 28 days (or 56 days in the case of Q8W dosing).

Note: If date of last dose of bimekizumab in the Maintenance Period + 28 days (or 56 days in the case of Q8W dosing) extends to a date beyond the final visit date in the Maintenance Period (including PEOT, but not including SFU), then this calculation reverts to:

- Final visit date in the Maintenance Period (including PEOT, but not including SFU) – date of first dose in the Maintenance Period + 1.

Note: For subjects who die, if date of last dose of bimekizumab in the Maintenance Period + 28 days (or 56 days in the case of Q8W dosing) extends to a date beyond the date of death, then this calculation reverts to:

- Date of death – date of first dose in the Maintenance Period + 1.

Time at risk (days):

- For subjects who continue into an open-label study (and, therefore, do not have the SFU visit in the feeder study): Final visit date in the Maintenance Period – date of first dose in the Maintenance Period + 1.
- For subjects who die prior to the final visit in the Maintenance Period: Date of death – date of first dose in the Maintenance Period + 1.
- For all other subjects, use the minimum of the following:
 - Date of last dose in the Maintenance Period – date of first dose in the Maintenance Period + 140 days.
 - Date of last clinical contact – date of first dose in the Maintenance Period + 1.

Note: This group could include subjects who discontinue the maintenance period early, subjects who complete the Maintenance Period as scheduled but choose not to continue into an open-label study, or subjects who are ongoing in the SFU period at the time of the data snapshot.

For subjects randomized to ADA/BKZ Q4W:

Study medication duration (days)

Only the duration of Bimekizumab treatment will be derived over this period as the summaries produced are for the BKZ Set (not including any adalimumab treatment).

- Date of last dose of bimekizumab on or after Week 24 – date of first dose on or after Week 24 + 28 days

Note: If date of last dose of bimekizumab + 28 days extends to a date beyond the final visit date in the Maintenance Period (including PEOT, but not including SFU), then this calculation reverts to:

- Final visit date in the Maintenance Period (including PEOT, but not including SFU) – date of first dose on or after Week 24 + 1.

Note: For subjects who die, if date of last dose of bimekizumab in the Maintenance Period + 28 days extends to a date beyond the date of death, then this calculation reverts to:

-
- Date of death – date of first dose on or after Week 24 + 1.

Time at risk (days):

- For subjects who continue into an open-label study (and, therefore, do not have the SFU visit in the feeder study): Final visit date in the Maintenance Period – date of first dose on or after Week 24 + 1.
- For subjects who die prior to the final visit in the Maintenance Period: Date of death – date of first dose on or after Week 24 + 1.
- For all other subjects, use the minimum of the following:
 - Date of last dose on or after Week 24 – date of first dose on or after Week 24 + 140 days.
 - Date of last clinical contact – date of first dose on or after Week 24 + 1.

Note: This group could include subjects who discontinue the Maintenance Period early, subjects who complete the Maintenance Period as scheduled but choose not to continue into an open-label study, or subjects who are ongoing in the SFU period at the time of the data snapshot.

10.2 Adverse events

An AE is any untoward medical occurrence in a subject or clinical investigation subject administered a pharmaceutical product that does not necessarily have a causal relationship with this treatment. An AE can therefore be any unfavorable and unintended sign (including an abnormal laboratory finding), symptom, or disease temporally associated with the use of a medicinal (investigational) product, whether or not related to the medicinal (investigational) product.

Adverse events will be coded according to the Medical Dictionary for Regulatory Activities (MedDRA version 19.0). For subjects who switch treatment during the study i.e. those randomized to BKZ Q4W/Q8W or ADA/BKZ, any adverse events that occur after initiation of the new treatment are attributable to the new treatment. If an adverse event occurs on the date of a treatment switch, the event is attributed to the original treatment. The only exception to this is if the AE fulfills the criteria for an anaphylactic reaction as defined in the bimekizumab safety topics of interest document. Specifically, this includes the following:

- Events that fulfill the anaphylaxis criteria for acute events (refer to Appendix A in section 12)
- Events with a reported term containing the term “hypersensitivity (SMQ)”
- Events with an HLT of “Administration site reactions NEC”
- Events with an HLT of “Injection site reactions”

10.2.1 Data considerations

Treatment-emergent AEs (TEAEs) are defined as those AEs that have a start date on or following the first dose of study treatment through the final dose of study treatment + 140 days

(covering the 20-week SFU period). If it is not possible (due to partial dates) to determine whether or not an AE is treatment-emergent then it will be assumed to be a TEAE.

The rules for imputing partial start or stop dates are outlined in Section 4.2.1.2.

If the intensity of an adverse event is unknown, it is considered as severe. If the relationship to study drug is missing, it is considered as related.

AEs will be presented as “number of subjects (percentage of subjects) [number of events]”. In this style of output, “[number of events]” will include all cases of an AE including repeat occurrences in individual subjects, while “number of subjects” will count each subject only once.

Subject time at risk represents the time a subject is at risk for having an AE. The definitions for subject time at risk (in days) are outlined in Section 10.1. These definitions will be used for exposure-adjusted AE summaries.

Selected AE summaries will include the exposure adjusted incidence rate (EAIR) with associated 95% confidence interval and the exposure adjusted event rate (EAER).

The EAIR is defined as the number of subjects (n) with a specific AE adjusted for the exposure and will be scaled to 100 patient-years:

$$EAIR = 100 \times n / \sum_{i=1}^N (T_{Exp(i)})$$

Where $T_{Exp(i)}$ is the exposure time and N is the number of subjects at risk.

If a subject has multiple events, the time of exposure is calculated to the first occurrence of the AE being considered. If a subject has no events, the total time at risk is used.

Exact Poisson 95% confidence intervals for incidence rates are calculated using the relationship between the Poisson and the Chi-square distribution (Ulm, 1990; Fay and Feuer, 1997):

$$LCL = \chi^2_{2n, \alpha/2} / 2$$

$$UCL = \chi^2_{2(n+1), \alpha/2} / 2$$

where n is the number of subjects with a specific AE for the incidence rate of interest and is the basis for the number of the degrees of freedom for the chi-square quantile for the upper tail probability χ^2 .

The EAER will be the number of AEs including repeat occurrences in individual subjects divided by the total time at risk scaled to 100 patient-years and calculated using:

$$EAER = 100 \times N_{AE} / \sum_{i=1}^N (T_{Risk(i)})$$

where N_{AE} is the total number of AEs, T_{Risk} is the time at risk for each subject, and N is the total number of subjects at risk.

No confidence interval will be computed for EAER.

Selected summaries for the subjects who switch from adalimumab to bimekizumab will be presented by time of onset (≤ 70 days or > 70 days from the final dose of adalimumab). Only events starting after the first dose of bimekizumab will be included.

70 days was chosen as it is approximately equal to five half lives of adalimumab.

Selected summaries, as specified in Section 10.2.2, will include the risk difference between bimekizumab and adalimumab. The risk difference is calculated as:

$$RD = IP_{BKZ} - IP_{ADA}$$

where IP_{BKZ} is the incidence proportion for the bimekizumab-treated group and IP_{ADA} is the incidence proportion for the adalimumab group. Note that incidence proportion simply refers to the percentage of subjects within the specified treatment group that experienced a given adverse event.

The standard error for the risk difference is calculated as follows:

$$SE_{RD} = \sqrt{\left(IP_{BKZ} \times \left(\frac{1 - IP_{BKZ}}{n_{BKZ}} \right) \right) + \left(IP_{ADA} \times \left(\frac{1 - IP_{ADA}}{n_{ADA}} \right) \right)}$$

where n_{BKZ} is the number of subjects in the bimekizumab-treated group and n_{ADA} is the number of subjects in the adalimumab group.

The corresponding confidence interval for the risk difference is as follows:

$$CI_{RD} = RD \pm Z_{1-\alpha/2} \times (SE_{RD})$$

where $Z_{1-\alpha/2}$ is the Z statistic for the corresponding level of alpha. For the risk difference confidence intervals calculated in this SAP, 1.96 will be used (corresponding to a two-sided alpha of 0.05 and 95% confidence interval). Risk difference and the corresponding confidence interval will be presented as a percentage.

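### Adverse event rates after the switch from adalimumab are split at 70 days, but the time at risk under them is not

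*SAP*

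**What the plan says.** Section 10.2.1 of the SAP states: "Selected summaries for the subjects who switch from adalimumab to bimekizumab will be presented by time of onset", with the cut at 70 days from the final adalimumab dose, about five adalimumab half-lives. It adds: "Only events starting after the first dose of bimekizumab will be included".

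Section 10.2.2 identifies the output: Week 24 to Week 56, BKZ Week 24 Set, subjects randomized to adalimumab, with the stated purpose of looking at events inside and beyond 70 days. Of the three summaries listed, two (TEAEs and serious TEAEs by SOC, HLT and PT) are per 100 subject-years. The end of the section requires EAIR with its interval, and EAER, in every summary on that scale.

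Section 10.2.1 fixes the denominator: "The definitions for subject time at risk (in days) are outlined in Section 10.1. These definitions will be used for exposure-adjusted AE summaries". EAER is the number of events "divided by the total time at risk scaled to 100 patient-years". For EAIR: "If a subject has no events, the total time at risk is used".

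For the ADA/BKZ Q4W arm, Section 10.1.4 defines time at risk once. Open-label entrants have "Final visit date in the Maintenance Period – date of first dose on or after Week 24 + 1". For subjects who neither enter that study nor die, it is the smaller of "Date of last dose on or after Week 24 – date of first dose on or after Week 24 + 140 days" and the time to last clinical contact. There is no separate definition for either 70-day window.

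**The concern.** The numerator is divided at 70 days and the denominator is not. A rate per 100 patient-years for early-onset events should rest on the time in which an early-onset event could occur. Divided by the whole post-switch period, both rates come out too low, and the early one far more so because its window is short.

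The early window is also why the split exists. Protocol 14.5.1 singles out the safety of switching for extra summaries, and the cut is placed so that residual adalimumab exposure falls in the first part. A reader comparing the two columns would see a reassuringly low early rate that comes from the arithmetic alone.

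**Working it through.** The plan gives no window-specific person-time or rate, so there is no stated figure to reproduce. Everything below follows from the dosing schedule and the Section 10.1.4 formulas.

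**Inputs (days after first study dose).** Protocol 7.2: final adalimumab at Week 23 = 161; first bimekizumab at Week 24 = 168; last bimekizumab at Week 52 = 364. Final visit at Week 56 = 392. The cut is 161 + 70 = 231.

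**Window lengths, on-schedule open-label entrant**
- Time at risk: 392 − 168 + 1 = 225 days.
- Early onset days: 169 to 231 = 63. The switch day is left out because Section 10.2 says "If an adverse event occurs on the date of a treatment switch, the event is attributed to the original treatment". The listed exceptions, such as injection site reactions, go to the new treatment and make it 64.
- Late onset days: 232 to 392 = 161.

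**EAER as written, relative to the true rate.** The ratio is window days divided by total days.

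| | Early | Late | Early:late if true rates are equal | Early:late if the true early rate is double |
|---|---|---|---|---|
| 63 early days | 63/225 = 0.280 | 161/225 = 0.716 | 63/161 = 0.391 | 0.783 |
| 64 early days | 64/225 = 0.284 | 0.716 | 64/161 = 0.398 | 0.795 |

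**Permitted visit windows (±3 days at Weeks 23 and 24, ±7 at Week 56)**
- Lowest: adalimumab on day 158, bimekizumab on 171, Week 56 on 399. Early 57, late 171, total 229. Early figure 57/229 = 0.249; equal-rate ratio 57/171 = 0.333.
- Highest: days 164, 165 and 385. Early 69, late 151, total 221. Early figure 69/221 = 0.312; ratio 69/151 = 0.457.

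**Completer who does not enter the open-label study.** Time at risk is min(364 − 168 + 140, 504 − 168 + 1) = 336 days.
- Early figure: 63/336 = 0.188.
- Late figure: 161/336 = 0.479 if events stop at Week 56, as Section 10.2.2 states for this table. If events to last dose + 140 days are counted, the late window has about 272 days: 272/336 = 0.81, with a ratio of about 63/272 = 0.23.

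**Mix of follow-up.** The open-label share f is not given. Assuming non-entrants complete treatment, the mean denominator is 225f + 336(1 − f).
- f = 1: 63/225 = 28%.
- f = 0.8: 63/247.2 = 25%.
- f = 0: 63/336 = 19%.

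With events to Week 56, the equal-rate ratio stays at 63/161 for any f, because both windows share one denominator.

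**EAIR.** Subjects without the event contribute their full time at risk, so for an uncommon AE nearly everyone contributes 225 days and the same fractions return. Example at a true 0.1 per year, early window:
- Probability of an event: 1 − exp(−0.1 × 63/365.25) = 0.0171.
- Mean time counted: about 0.0171 × 31.4 + 0.9829 × 225 = 221.7 days = 0.607 years.
- Rate shown: 0.0171/0.607 = 0.028 per year, 28% of the truth.

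Across the ways of counting that were checked, at true rates up to 0.1 per year, EAIR is 28–29% early and about 70–72% late. For commoner AEs it depends on how subjects with an early event are treated. A simulation at a true 100 per 100 patient-years (150 subjects, 64 early days, early cases allowed to be late cases) gave about 30 early and 67 late. Window-specific time gave about 100 in each.

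**Illustration.** Assumed: 150 switchers on schedule, all entering the open-label study, 200 TEAEs per 100 patient-years in both windows.
- Person-years: 150 × 225/365.25 = 92.4 in total; 150 × 63/365.25 = 25.9 early; 150 × 161/365.25 = 66.1 late.
- Expected events: 51.7 early, 132.2 late.
- Shown as written: 51.7/92.4 = 56 and 132.2/92.4 = 143 per 100 patient-years.
- At an assumed 100 the table shows 28 and 72; at an assumed 300, 84 and 215.
- For scale, an exact Poisson interval for 52 events in 25.9 person-years is 150–264, so the printed 56 lies far outside sampling error. The SAP computes no interval for EAER, and this one treats repeat events as independent.

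**The case against.** The strongest reply is that this is missing detail rather than a wrong instruction. Section 10.2.1 also describes time at risk as the time in which a subject can have an AE, and a programmer working from that sentence would cut the person-time at 70 days. The text also never says outright that EAIR and EAER are computed within each window. One overall post-switch rate beside split counts might be thought to satisfy Section 10.2.2, and the table shells that could settle it are not in the documents. Section 10.1.4 is headed for the BKZ Set, whereas this table uses the BKZ Week 24 Set.

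These readings depart from the explicit text. The summaries presented by onset are the per-100-subject-years tables; every such table must carry both rates; and the rule for both names the Section 10.1 definitions and total time at risk. Elsewhere Section 10.1 matches person-time to the reporting period (initial, through Week 24, maintenance, and Q4W versus Q8W within one arm), so the 70-day windows stand out as the gap. The difference in set name is minor, because the switchers are the same people.

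What stands is the limit on consequence. The tables are descriptive and no early-versus-late contrast is planned. Counts and percentages appear alongside, so an attentive reader could notice the mismatch. Serious TEAEs are probably too few for the distortion to be visible.

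**Conclusion.** The point holds. Applied as written, neither figure is the event rate in its window. On schedule, EAER shows 28% of the true early rate and 72% of the true late rate, so equal rates look like 0.39–0.40 and a true doubling soon after the switch looks like 0.78–0.80. Within the permitted visit windows the equal-rate ratio for an open-label entrant is 0.33–0.46, never near 1. EAIR is biased the same way.

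The 28%, 72% and 0.39 figures rest only on the dosing schedule and entry to the open-label study. The 25% and 19% early figures also depend on the open-label share, which is not given, and the event counts in the illustration are assumed. The plan should be corrected, because exposure-adjusted TEAEs and SAEs are secondary safety variables and switch safety is a declared interest. The unsplit post-switch rate, counts and percentages, the 70-day laboratory summaries and all randomized comparisons are unaffected.

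**What to change.** Add to SAP Section 10.1.4, for the ADA/BKZ Q4W arm:

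- **Early time at risk:** from the first bimekizumab dose to the earlier of final adalimumab dose + 70 days and the end of time at risk.
- **Late time at risk:** from then to the end of time at risk, for subjects still at risk only, ending where the table's event period ends (Week 56 under Section 10.2.2).

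In Section 10.2.1, state that EAIR and EAER in each window use these times and that the EAIR clock starts at the start of the window. Also state whether a subject with an early event can count again as a late case. Section 10.2.2 should use the same origin for the 70 days as Sections 10.2.1 and 10.3, the final adalimumab dose, since its wording refers to the treatment switch.

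The cost is a few lines of text and derivation code. No new data are needed, and the randomized tables through Week 24 do not change.

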4.2.2 Secondary safety variables

- TEAEs adjusted by duration of subject exposure to study treatment
- SAEs adjusted by duration of subject exposure to study treatment
- TEAEs leading to withdrawal adjusted by duration of subject exposure to study treatment

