The following summary will be provided through initial and maintenance treatment period for the BKZ Set:

- Incidence of TEAEs per 100 subject years by SOC, HLT, and PT and by Time of Onset Relative to Anti-bimekizumab Antibody Status

In addition, all summaries of TEAEs based on “100 subject years” should include EAIR (with 95% confidence interval) and EAER.

The tables with risk differences will also be accompanied by figures (dot plots) which show the incidence of the adverse events and corresponding 95% risk difference confidence intervals. These will be ordered by descending order of risk difference (bimekizumab vs adalimumab).

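### The SAP's exact Poisson confidence limits for exposure-adjusted incidence rates use the same chi-square tail twice and are never put on the rate scale

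*SAP*

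**What the plan says.** SAP Section 10.2.1 defines the EAIR as 100 times the number of subjects with the event, divided by summed exposure time. Exposure stops at the first occurrence for subjects with the event. On the interval it says: "Exact Poisson 95% confidence intervals for incidence rates are calculated using the relationship between the Poisson and the Chi-square distribution". The limits are then printed as "LCL = \chi^2_{2n, \alpha/2} / 2" and "UCL = \chi^2_{2(n+1), \alpha/2} / 2". The explanation below them reads "where n is the number of subjects with a specific AE for the incidence rate of interest" and adds that n "is the basis for the number of the degrees of freedom for the chi-square quantile for the upper tail probability". Nothing there gives the two limits different tails, and no exposure term or factor of 100 appears in either limit.

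SAP Section 10.2.2 applies the interval widely: every TEAE summary per 100 subject years "should include EAIR (with 95% confidence interval) and EAER". The rates behind it are secondary safety variables. Protocol Section 4.2.2 lists "TEAEs adjusted by duration of subject exposure to study treatment", and the same adjustment for SAEs and for TEAEs leading to withdrawal.

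**The concern.** There are two separate errors.

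- **Tails.** The lower limit of an exact Poisson interval comes from the lower alpha/2 quantile of chi-square with 2n degrees of freedom. The upper limit comes from the upper alpha/2 quantile with 2(n+1) degrees of freedom. The SAP uses one tail for both, so the two limits differ only by two degrees of freedom and bracket a narrow strip on one side of n.
- **Scale.** Half a chi-square quantile bounds the expected count. It does not bound a rate per 100 patient-years.

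The affected output includes the overall and serious TEAE tables (each produced in five ways under SAP Section 10.2.2), the discontinuation table (four ways), and the tables per 100 subject years for the safety topics in SAP Section 10.2.3. Many rows there will have few events, which is where a reader relies most on the interval.

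**Working it through.** **Inputs.** The formulas, the 95% level and the EAIR definition come from SAP Section 10.2.1. Alpha is 0.05 two-sided, as that section states for the risk difference. The SAP gives no worked interval, so the figure to reproduce is the nominal 95%.

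**Step 1: one case, n = 10, count scale.** The degrees of freedom are 2n = 20 and 2(n+1) = 22.

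| Quantile | df 20 | df 22 |
|---|---|---|
| Lower-tail probability 0.025 | 9.591 | 10.982 |
| Upper-tail probability 0.025 | 34.170 | 36.781 |

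- Correct: 9.591/2 = 4.80 to 36.781/2 = 18.39.
- As printed, upper tail for both: 34.170/2 = 17.08 to 36.781/2 = 18.39.
- Lower tail for both: 9.591/2 = 4.80 to 10.982/2 = 5.49.

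**Step 2: other counts.**

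| n | Correct | Upper tail for both | Lower tail for both |
|---|---|---|---|
| 1 | 0.03 to 5.57 | 3.69 to 5.57 | 0.03 to 0.24 |
| 2 | 0.24 to 7.22 | 5.57 to 7.22 | 0.24 to 0.62 |
| 5 | 1.62 to 11.67 | 10.24 to 11.67 | 1.62 to 2.20 |
| 30 | 20.24 to 42.83 | 41.65 to 42.83 | 20.24 to 21.06 |

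For every n from 1 to 60, both readings exclude n itself. No choice of a single convention rescues the formula.

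**Step 3: coverage on the count scale.** Sum the Poisson probabilities of all counts whose interval contains the true mean, with the lower limit set to 0 at n = 0.

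| True mean | Correct | Upper tail for both | Lower tail for both |
|---|---|---|---|
| 1 | 98.1% | 36.8% | 6.1% |
| 2 | 98.3% | 13.5% | 3.6% |
| 5 | 98.0% | 3.4% | 1.8% |
| 10 | 97.5% | 1.9% | 1.3% |
| 20 | 95.7% | 1.8% | 1.3% |
| 50 | 95.3% | 1.0% | 0.8% |
| 100 | 95.5% | 0.6% | 0.6% |

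The stated 95% is not reproduced under either reading. It is reproduced, conservatively, once opposite tails are used.

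**Step 4: the missing scaling, with the tails corrected.** For n = 10 the unscaled limits stay at 4.80 to 18.39 whatever the exposure. The documents give no exposure totals, so a range is assumed. The 138.0 patient-years correspond to the planned 300 bimekizumab subjects each followed for 24 full weeks (300 × 24 × 7 / 365.25), ignoring censoring at first event.

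| Patient-years | EAIR = 100 × 10 / PY | Unscaled limits | Limits × 100 / PY |
|---|---|---|---|
| 50 | 20.00 | 4.80 to 18.39 | 9.59 to 36.78 |
| 138.0 | 7.25 | 4.80 to 18.39 | 3.48 to 13.33 |
| 276 | 3.62 | 4.80 to 18.39 | 1.74 to 6.66 |
| 400 | 2.50 | 4.80 to 18.39 | 1.20 to 4.60 |

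The unscaled interval misses the EAIR at 50, 276 and 400 patient-years. It is right only when total exposure is exactly 100.

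**The case against.** The strongest reply is that the intended method is clear. The SAP names the exact Poisson interval and cites sources for it, so a programmer may well use a standard routine and never follow the subscripts. The EAIR definition just above also makes multiplication by 100 over exposure the only sensible completion. This stands to the extent that the documents cannot show any table to be wrong. They do show that the written rule contradicts the method it names: code that follows the rule gives wrong limits, and correct code does not match the text it is validated against.

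A second reply is that a 1− may have been lost from the lower-limit subscript when the PDF was read. Formula transcription is uneven: the standard error of the Mantel-Haenszel risk difference is bracketed differently in SAP Section 8.1.2 and in the log of SAP Amendment 1. This is possible but not shown. The 1−α/2 subscript in the risk-difference interval of the same section came through intact, and a lost 1− would not explain the absent exposure term.

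Three limits on the point are fair:

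- Under each reading one limit is correct apart from scaling: the upper limit with upper tails, the lower limit with lower tails.
- At n = 0, with the lower limit taken as 0, the upper-tail reading gives 0 to 3.69, which is right before scaling. For this reason coverage is less extreme for very rare events under that reading: 78% at a mean of 0.25 and 61% at 0.5, still well short of 95%.
- The intervals are descriptive, and limits that exclude their own estimate should be noticed in output review.

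**Conclusion.** The concern holds. Applied as printed, the formula gives intervals that exclude the observed count at every n from 1 to 60 under either tail convention. Count-scale coverage for true means of 5 to 100 is 0.6% to 3.4% with upper tails and 0.6% to 1.8% with lower tails, instead of at least 95%. Separately, the limits are not on the scale of the rate they accompany unless exposure happens to be 100 patient-years.

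The conclusion takes the formula as it reads in the SAP and assumes alpha = 0.05. Only the rate-scale illustrations depend on assumed exposure. EAIR and EAER point estimates, event counts, risk differences, the co-primary tests and the sample size are untouched. Because the intervals go into the secondary safety tables, the text should be corrected before those tables are reported.

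**What to change.** Replace the two formula lines and the sentence on the tail in SAP Section 10.2.1. Write ΣT for the exposure sum already used in the EAIR, with time stopped at first occurrence, and let χ²(p; df) be the quantile with lower-tail probability p:

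- LCL = 100 × χ²(α/2; 2n) / (2 × ΣT), set to 0 when n = 0
- UCL = 100 × χ²(1 − α/2; 2(n+1)) / (2 × ΣT)

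State α = 0.05. Then check the macro with a known case: n = 10 and ΣT = 100 patient-years must return 4.80 to 18.39, and n = 10 with ΣT = 276 must return 1.74 to 6.66. The cost is two lines of SAP text and one program check, with a rerun of the affected tables if the macro followed the printed formula. No additional data are needed.
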